2. PROTOCOL SUMMARY

Name of Drug(s)	Lidocaine hydrochloride (Xylocaine®-MPF); methylprednisolone sodium succinate (SOLU-MEDROL®)	
Treatment Group/Sample Size	10 total subjects	
Design	Open-label, non-randomized study	
Estimated Length of Subject Involvement	90 days	
Route of Administration	Intra-arterial	
Regimen	40 mg lidocaine/20mg methylprednisolone co-administered into each middle meningeal artery (left and right side) once	
Primary Objective	This study will evaluate the safety of a co-administration of intra-arterial lidocaine and methylprednisolone for patients with intractable migraine. In addition, an examination of pain-related symptomatic relief per pain score scales will be assessed.	
Study Population	10 adults over the age of 18 with a diagnosis of intractable migraine without aura, defined as failure of four treatment trials, will be enrolled in the study if they meet inclusion and exclusion criteria and are willing to participate in the study.	
Multicenter	No	
Blinding	None/Open-label	
Randomization	None/Non-randomized	
Primary Safety Variable	Adverse Events	
Primary Efficacy Variable	y Variable Difference in pre- and post-drug MIDAS, 4-point verbal pain scale, and 11-point numeric pain scale scores.	

3. STUDY RATIONALE

3.1. Intractable Migraine

Treatment-refractory intractable migraine is a challenging clinical condition. The Refractory Headache Survey estimated intractable migraine prevalence to be on average between 5-10% of the neurologic specialists' patient consensus.¹ Failure of adequate control of symptoms under standard therapy causes significant pain burden, migraine-related disability, and impaired quality of life.¹ Consequently, new approaches to intractable migraine treatment have potential to improve patient outcomes.

Previous case reports describe positive clinical experiences from initial attempts at intraarterial lidocaine administration into the middle meningeal artery, including reduced migrainerelated disability, subjective reports of pain improvement, and reduced pain scores.^{2,3} Two severe migraine patients received intra-arterial doses of 40 mg lidocaine and 20 mg methylprednisolone in the middle meningeal artery, and reported subjective improvement in headache intensity after 24 hours.³ Qureshi et al. (2021) found that in a study of four patients, intra-arterial lidocaine administered in 2 mg/ml increments up until 50 mg to bilateral middle meningeal arteries resulted in large decrease in pain score (from greater than 5/10 to less than 5/10) and subjective reports of decreased headache intensity in four patients.² Moreover, these initial experiences have not reported any serious adverse effects associated with intra-arterial lidocaine administration. This is in concordance with the safety profile of intra-arterial lidocaine administration in the peripheral circulation.^{4,5,6} However, the patient sample was limited, and a formal phase 1 trial is yet to be conducted.

Results of this study will demonstrate the safety profile of this drug co-administration, and it will serve as the basis for future larger-scale investigations to evaluate efficacy. Safety and efficacy of the administration will expand available treatment options for intractable migraine patients.

We propose to conduct a pilot, non-randomized, open-label phase 1 clinical trial to characterize the safety of intra-arterial injection of lidocaine and methylprednisolone into the middle meningeal artery for treatment of intractable migraine.

Mechanistically, lidocaine inhibits ionic fluxes across the neuronal membrane necessary for initiating and propagating electrical impulses conducting pain signals.¹² Consequently, inhibited neuronal signaling blocks the pain sensation associated with migraines. Steroids exert a multi-organ anti-inflammatory response, including within the brain, through cell signaling inhibition of inflammatory markers.¹³ Hence, steroids likely are therapeutic for migraines, since they counteract the neurogenic inflammation associated with migraines.^{10,11}

Prior case reports in six patients describe initial clinical experiences following intraarterial lidocaine and methylprednisolone administration into the middle meningeal artery.^{14,15} These patients reported favorable symptomatic relief, including reduced disability and subjective pain improvement, following the drug co-administration. Moreover, there were no serious adverse events reported in both investigations.

Consequently, the co-administration of two commercially-available drugs demonstrates potential to provide patients relief for a clinically-challenging diagnosis. Although early experience suggests favorable safety and efficacy, formal analysis in this phase 1 study and other subsequent investigations will evaluate the drug as a potentially viable treatment option for patients with treatment-resistant migraines, and thus improve their pain and qualify of life. Additionally, this phase 1 study will facilitate global assessment of practices, research procedures, and recruitment practices, with the intention of use as the basis for multicenter support for future clinical trial phases.

3.3. **Alternatives to Study Drug**

The alternative for not taking part in this study is to continue current course of care, which may include continuing current medications (oral or infusion) for intractable migraine. Other medications are available for this condition, including antiepileptic drugs, beta-blockers, antidepressants, angiotensin receptor blockers/angiotensin-converting enzyme inhibitors, nonsteroidal anti-inflammatory agents (NSAIDS), ergots, triptans, analgesics (i.e., acetaminophen), botulinum toxin injections, or calcitonin gene-related peptide monoclonal antibodies.

¹² NDA 006488 lidocaine hydrochloride injection, solution.

https://dailymed.nlm.nih.gov/dailymed/drugInfo.cfm?setid=ba082c2f-64f4-419d-9c88-74f203316e17 ¹³ NDA 011856 methylprednisolone sodium succinate for injection, USP.

3.4. Risk / Benefit Assessment

Risks associated with intra-arterial administration route includes rare adverse events related to intravascular access, including allergic response to contrast agents, vessel injury, access site hematoma, and infection. Risks will be mitigated by implementation of institutional standard practices protocol, including standardized procedures in the event of an interventional accessrelated complication.

For example:

- Protocols are in place to obtain an ultrasound study if access site hematoma is suspected post-administration of the study drug.
- In case of unexpected, severe contrast allergy, a combination of intravenous fluids, diphenhydramine, hydrocortisone, and/or adrenaline will be administered.

Risks associated with sedative mediations used for "twilight anesthesia"/monitored anesthesia care (MAC) include the risk of excessive or prolonged sedation, potentially requiring intubation. Risks will be mitigated by using minimal sedation necessary to safely obtain interventional access.

Risks associated with methylprednisolone administration include teratogenic effect on unborn fetuses. Risks will be mitigated by pre-treatment urine pregnancy test to screen for pregnancy in patients of child-bearing age.

Risks associated with bilateral versus unilateral injection are present, including from catheterization and dose toxicity. Intra-arterial navigation to obtain access to the contralateral middle meningeal artery present similar risks associated with intravascular access, as described above. Although risk of contralateral access is present, this phase 1 protocol uses a bilateral injection approach, as unilateral treatment has only been shown to be effective in patients with migraine-related symptoms that are exclusively localized to one side.¹ Although risk of toxicity from dose quantity is present, the dosages outlined in this study are well below the threshold for toxicity per the Prescribing Information. Moreover, a prior case report using lidocaine hydrochloride/methylprednisolone sodium succinate administered intra-arterially into the middle meningeal artery bilaterally for the indication of migraine and headache, using the dosing approach described in Section 6.1.5/Amendment #2, demonstrated no safety concerns in two patients.¹⁶ In a separate dose-escalation study in four patients, intra-arterial lidocaine was administered in 2mg/mL increments until 50 mg per middle meningeal artery (100mg lidocaine total), and there were no adverse effects reported.¹⁷ Based on prior clinical experience in the same or greater dosing amount with the same route of administration for the same indication, the risk for toxicity is expected to be minimal.

Benefits to subjects for the research include potential resolution of intractable migraine symptoms following treatment. Potential benefit also includes presenting an alternative, minimally invasive pharmacologic approach to intractable migraine to substitute chronic, frequent treatment with oral medications.

No specific methylprednisolone-related risks are anticipated for the investigational dosing amount and route. The following are potential complications for methylprednisolone use per Section 5 (WARNINGS AND PRECAUTIONS) for the Prescription Drug Labeling of NDA 011856. Complications with methylprednisolone treatment are dependent on dosage size, duration, and route of administration. Methylprednisolone has been associated with rare serious neurological adverse events, including spinal cord infarction, paraplegia, quadriplegia, cortical blindness, and stroke, with epidural administration. There have been rare reports of anaphylactoid reactions. Large doses of corticosteroids have been associated with elevated blood pressure and increased potassium and calcium excretion. After recent myocardial infarction, there has been a suggested association between drugs within the corticosteroid pharmacologic class and left ventricular free wall rupture. Chronic methylprednisolone use is associated with hypothalamic-pituitary adrenal axis suppression, Cushing's syndrome, and hypoglycemia. High doses of cyclic, pulsed methylprednisolone administration are associated with toxic acute hepatitis. Corticosteroid use is associated with increased susceptibility to infections, including fungal infections.

Other risks of participation include very rare adverse events related to route of administration, including allergic response to agents, vessel injury, access site hematoma, and infection.

4. STUDY OBJECTIVES

4.1. Primary Objective

Primary outcome is safety of the lidocaine and methylprednisolone co-administration intra-arterially into the middle meningeal arteries. The endpoints that will be analyzed to examine this outcome include: incidence of all adverse events; incidence of adverse events attributed to the study drug; and incidence of any serious adverse events.

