4.2. Secondary Objectives

Efficacy is a secondary outcome that will be examined. The endpoints for evaluation include difference in MIDAS, 4-point verbal pain scale, and 11-point numeric pain scale scores prior to drug administration and 1 week, 6 weeks, and 3 months after drug administration.

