5. STUDY DESIGN

5.1. General Approach for Evaluation of Treatment

This study will be a non-randomized, open-label phase 1 clinical trial. Participants above the age of 18 years who have an established diagnosis of intractable migraine (defined as failure of four other pharmacologic agents) and are active patients at our institution (i.e., have an appointment with a neurologic care provider during the enrollment period) will be offered enrollment. Either intolerance or side effects requiring early discontinuation or adequate trial at therapeutic dose without relief constitutes failure of therapy.

A neurological provider will perform a baseline assessment of enrolled patient's medical history and symptom scale scores, including MIDAS, 4-point verbal pain scale, and 11-point

numeric pain scales (Appendix G). An experienced neurointerventional co-investigator will inject 20 mg methylprednisolone and 40 mg lidocaine into the middle meningeal artery bilaterally. Each patient will receive a total of two doses of the 40mg lidocaine/20mg methylprednisolone co-administration of drugs (i.e., one dose administered within the left middle meningeal artery, and the other dose in the right middle meningeal artery). Immediate post-operative clinical evaluation, and evaluation at subsequent follow-up appointments with a neurological provider will involve assessment of neurological functional status, symptom scores, and occurrence of any associated adverse event at 1 week, 6 weeks, and 3 months. To evaluate the primary safety outcome, data will be analyzed to yield the prevalence of any adverse event, treatment-related adverse events, and serious and/or fatal adverse events. Data comparing pairwise differences in pre- and post-drug changes in symptom scores at 1-week, 6-week, and 3-month follow-up clinical encounters will be analyzed to assess secondary efficacy outcome.

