5.3. Number of Subjects to be Evaluated

Up to 10 patients will be evaluated. Sample size was determined off of norms for phase 1 trials, as there lacks sufficient data to conduct a power analysis. Patients who are lost to follow-up and/or withdraw early from the study will not be replaced.

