8. DATA SAFETY MONITORING

8.1. Safety Monitoring Plan

Data safety monitoring will be undertaken jointly by the Institutional Review Board and Investigator, including training all co-investigators to report research-related adverse events to Investigator within 12 hours. A safety report to the Institutional Review Board after either

reaching half of anticipated enrollment (10 subjects) or eight months following trial start, whichever event occurs first, will be prepared.

An adverse event (AE) is any untoward medical occurrence in a clinical investigation of a patient administered a pharmaceutical product and that does not necessarily have a causal relationship with the treatment. An AE is therefore any unfavorable and unintended sign (including an abnormal laboratory finding), symptom or disease temporally associated with the administration of an investigational product, whether or not related to that investigational product. An unexpected AE is one of a type not identified in nature, severity, or frequency in the current Prescribing Information or of greater severity or frequency than expected based on the information in the Prescribing Information.

The Investigator will probe, via discussion with the subject, for the occurrence of AEs during each subject visit and record the information in the site's source documents. Adverse events will be recorded in the patient study records. Adverse events will be described by duration (start and stop dates and times), severity, outcome, treatment and relation to study drug, or if unrelated, the cause.

AE Severity

The National Cancer Institute's Common Terminology Criteria for Adverse Events (CTCAE) Version 3.0 will be used to assess and grade AE severity, including laboratory abnormalities judged to be clinically significant. The modified criteria can be found in the study manual. If the experience is not covered in the modified criteria, the guidelines shown in Table 2 below should be used to grade severity.

Severity (Toxicity Grade)	Description
Mild (1)	Transient or mild discomfort; no limitation in activity; no
	medical intervention or therapy required. The subject may be
	aware of the sign or symptom but tolerates it reasonably well.
Moderate (2)	Mild to moderate limitation in activity, no or minimal medical
	intervention/therapy required.
Severe (3)	Marked limitation in activity, medical intervention/therapy
	required, hospitalizations possible.

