9. STATISTICAL METHODS AND CONSIDERATIONS

9.1. Analysis Plan

An intention to treat analysis will be performed. Prevalence of any adverse event, treatment-related adverse events, and serious and/or fatal adverse events will be calculated. Secondary analyses assessing pairwise differences in pre- and post-interventional changes in symptom scores will also be performed to identify trends and as the basis for future power analyses. Categorical variable data will be summarized as frequencies with Agresti-Coull intervals as applicable. Quantitative variable data will be summarized as medians with interquartile ranges. Spearman's rank correlation coefficient, two-sided Student's t-test, chi-square tests, and nonparametric equivalences may be conducted at 0.05 significance level.

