9.2. Interim Analysis

One interim analysis is planned for formal evaluation of safety during phase 1. Interim analysis will be performed when a total of 10 patients (50%) have completed Study Visit 3 (1 week follow-up after study treatment).

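### The primary safety endpoints need a stated start, end and onset split, and the one stated window (for SAEs) starts too late to cover the access and sedation steps

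*Combined protocol and SAP*

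**What the plan says.** **Endpoints.** Section 4.1 lists three primary safety quantities: "incidence of all adverse events; incidence of adverse events attributed to the study drug; and incidence of any serious adverse events". It attaches no period to any of them. Section 4.2, directly after it, does fix times for the secondary efficacy endpoints: "prior to drug administration and 1 week, 6 weeks, and 3 months after drug administration".

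**Summary.** Section 5.1 says "data will be analyzed to yield the prevalence of any adverse event, treatment-related adverse events, and serious and/or fatal adverse events", and Section 9.1 says "Prevalence of any adverse event, treatment-related adverse events, and serious and/or fatal adverse events will be calculated". For intervals, Section 9.1 adds: "Categorical variable data will be summarized as frequencies with Agresti-Coull intervals as applicable". No table by time of onset is planned.

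**Collection.** Section 8.1 sets a period for SAEs only, from after study drug administration to the final visit. It sets none for non-serious events. It does require timing for every event: "Adverse events will be described by duration (start and stop dates and times), severity, outcome, treatment and relation to study drug". Under Section 6.4 the diary captures adverse events for four weeks before and three months after treatment.

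**Exposure and early observation.** Treatment is one session (Section 2). Section 7.1 builds in waits of 2 and 5 minutes to look for toxicity and at least 4 hours of monitoring afterwards. Section 3.4 lists risks of vascular access and of sedation.

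**Interim.** Section 9.2 times the safety look by patients who "have completed Study Visit 3 (1 week follow-up after study treatment").

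**The concern.** Incidence and prevalence are different quantities. Incidence counts new onsets in a period; prevalence counts what is present, including conditions that began earlier. In patients with chronic symptoms and a pre-treatment diary, the two can give different counts from the same records, and two analysts could each follow the text and report different primary results.

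In an uncontrolled trial of a single exposure, closeness in time to that exposure is one of the main pieces of evidence separating harm from coincidental illness. A single figure per endpoint does not show it. An event during the procedure and an unrelated one on day 80 count alike in the all-AE figure, and likewise in the SAE figure if both are serious.

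The start of the SAE period raises a separate problem. Arterial access, catheterisation and sedation come before the first injection. They are part of what the patient undergoes in order to receive the treatment, and the protocol names their risks, yet an SAE arising there falls before the stated collection period opens.

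**Working it through.** The documents give no safety rate, precision target or power, so there is no figure of the plan to reproduce. On sample size Section 5.3 says only: "Sample size was determined off of norms for phase 1 trials, as there lacks sufficient data to conduct a power analysis".

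**1. Which endpoint has which window**

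| Endpoint | Start stated | End stated | Split by onset |
|---|---|---|---|
| Any AE | No | No | No |
| Drug-attributed AE | No | No | No, but attribution considers timing |
| SAE | After drug administration (8.1) | Final visit (8.1) | No |

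**2. How far later events can mask acute harm in the all-AE figure**

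Inputs, all assumed because the documents give none:
- *a*: risk of an acute event from the procedure, 10% or 30%.
- *B*: proportion with at least one unrelated event over 12 weeks, at a constant rate. Unrelated risks of 5%, 10%, 20% or 30% per 4 weeks give B = 1 − (1 − b)³ = 14%, 27%, 49% or 66%. Means of 0.5, 1 or 2 events per 12 weeks give B = 1 − exp(−L) = 39%, 63% or 86%.

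Formulas:
- 12 weeks: 1 − (1 − a)(1 − B). Acute harm adds a(1 − B).
- Week 1: 1 − (1 − a)(1 − B)^(1/12). Acute harm adds a(1 − B)^(1/12).

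Percentage points added by acute harm:

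| B over 12 weeks | a = 10%: 12 weeks | a = 10%: week 1 | a = 30%: 12 weeks | a = 30%: week 1 |
|---|---|---|---|---|
| 14% | 8.6 | 9.9 | 25.7 | 29.6 |
| 27% | 7.3 | 9.7 | 21.9 | 29.2 |
| 39% | 6.1 | 9.6 | 18.2 | 28.8 |
| 49% | 5.1 | 9.5 | 15.4 | 28.4 |
| 63% | 3.7 | 9.2 | 11.0 | 27.6 |
| 66% | 3.4 | 9.1 | 10.3 | 27.4 |
| 86% | 1.4 | 8.5 | 4.1 | 25.4 |

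In patients, with B = 49% and a = 10%: over 12 weeks the expected count is 5.4 of 10 with acute harm and 4.9 without. Through week 1 it is 1.5 against 0.5.

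**3. What 10 patients can show**

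The Agresti-Coull interval (95% assumed, since no level is stated) uses ñ = 10 + 1.96² = 13.84 and p̃ = (x + 1.92)/13.84, with limits p̃ ± 1.96√(p̃(1 − p̃)/ñ).
- 0/10: 0.139 ± 0.182, or −4% to 32%.
- 1/10: 0.211 ± 0.215, or −0.4% to 43%.
- 3/10: 0.356 ± 0.252, or 10% to 61%.
- 10/10: 0.861 ± 0.182, or 68% to 104%.

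At the extremes the limits leave the 0–100% range, so the plan should say that they are truncated. An acute event with 10% risk is seen at least once with probability 1 − 0.9¹⁰ = 65%.

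**The case against.** The strongest reply is that timing already enters a primary endpoint. In Section 8.1 the categories *Probably* and *Possibly* require a plausible time sequence; *Definitely* does too, unless its alternative of known toxicity applies. The drug-attributed endpoint is therefore meant to remove unrelated late events. This stands in part, and a reader who infers that the plan discards timing goes too far. But attribution is made open-label, *Unrelated* demands certainty, and no category lies between it and *Possibly*, so doubtful late events have nowhere clear to go. The all-AE and SAE endpoints count events whatever their cause.

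A second reply is that the windows are not wholly missing. This also stands: SAEs have a collection period, and Section 5.1 sets assessments immediately after the procedure and at 1 week, 6 weeks and 3 months. The AE definition in Section 8.1 refers to events linked in time to administration, and the Visit 2 diary review in Section 7.2.2 mentions only migraine episodes. That points towards leaving pre-treatment events out, but no number of days is given and nothing says so.

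Third, a reader might say that acute harm is diluted. It is not lowered: every acute event stays in the numerator of a cumulative proportion. What shrinks is the increment over a background that this trial cannot estimate, so masking is the accurate word.

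Fourth, it is tempting to infer that interim and final rates are invalidly compared. No such comparison is planned, and Section 9.2 says when the look takes place, not that data are cut at week 1. Nor does that look supply a week-1 figure in the final report.

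Finally, with 10 patients and recorded onset times, a split could be made later. That is true, but Section 9 promises neither a listing nor an onset table, and a cut chosen after seeing the events is weaker evidence than one fixed beforehand.

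**Conclusion.** The concern holds in a limited form. The naming of the primary quantities is inconsistent, non-serious events have no stated start or end, no onset split is planned, and the SAE period begins after the procedural steps that precede injection. These four points rest on the text alone.

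The size of the masking rests on assumptions: a constant unrelated event rate, independent of acute events, and the ranges of *a* and *B* above. The direction holds for any non-zero unrelated rate; the amount does not. The 30% columns are the favourable case. At 10% the gain from looking at week 1 is from about 1 point (9.9 against 8.6) to about 7 points (8.5 against 1.4), or less than one patient in 10. The effect falls mainly on the all-AE endpoint, less on SAEs if these are fewer, and least on drug-attributed events.

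The documents do not support a claim that the safety data are lost or that the trial could not detect acute harm: dates, times and relatedness are all recorded. What is at stake is a primary result defined before the data are seen, with its timing evidence visible and procedural SAEs inside the count. That merits a change before analysis.

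**What to change.** - **Sections 4.1, 5.1 and 9.1.** Use incidence throughout. Define each quantity as the proportion of patients who start the procedure and have at least one event with new onset from the start of the procedure to Visit 5. Also report it for onset up to Visit 3 (week 1) and for onset after Visit 3. Give counts and Agresti-Coull intervals truncated to 0–100%. State the denominator, because Section 9.1 speaks only of intention to treat. Note that a patient with events in both periods counts in each.
- **Section 8.1.** Reconcile the start of SAE collection with this window, and give non-serious events the same start and end. Diary events from before the procedure then serve as baseline only.
- **Section 9.2.** Use the week-1 window for the interim safety summary. The trigger there, 10 patients described as 50%, implies 10/0.5 = 20 patients, against at most 10 in Sections 2 and 5.3. Section 8.1 has a similar wording. These passages must be reconciled for the look to have a defined timing.

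**Cost.** Wording in five sections and extra table columns. Onset dates and times are already collected; the only added collection is of SAEs between the start of the procedure and the first injection. The ±2-day visit window lets the week-1 cut fall between days 5 and 9, which is acceptable for a descriptive split. The split will not give precise rates in 10 patients and should not be presented as a test.
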